## 9.2. 12-month Phone Assessments

The following assessments will be collected via phone at 12 months ( $\pm$  30 days) post procedure:

- Assess any changes to medications
- Adverse event inquiry (specific to adverse events related to the MANTA leg and/or a MANTA related adverse event between 30 days and 12 months)
- Target Femoral access site assessment question
- Any subsequent secondary interventions since the 30-day visit (For example, any new surgical or percutaneous interventions post the index large bore procedure that occurred on the femoral artery of the MANTA (ipsilateral) leg, such as percutaneous coronary intervention (PCI), through the 12 month follow-up phone call.)

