6.7 Adverse Events and Device Deficiencies

Adverse events (AEs) and device deficiencies will be collected throughout this trial. AEs will be classified using the MedDRA coding system and will be summarized by System Organ Class and Preferred Term.

Adverse events that are determined to be related to the device or procedure (“associated with the target artery and/or the ipsilateral leg (not the contralateral side”) will be sent to the CEC for adjudication. The exact process will be finalized in the CEC charter. The CEC will adjudicate procedure and device relatedness of these events and whether events met an LBAR Major or Minor Complication. These adjudications will overrule investigator classifications for summarizing data.

For relatedness, classifications of Causal/Definite, Probably, Possible and Unknown (if any) will be considered related.

AEs will be summarized by count and proportion of subjects experiencing one or more events by seriousness, severity, device and procedure relatedness, and time period (day 0 (procedure)-discharge, discharge-30 days, 0-30 days, 31-60, 61-180 days, and 181-study exit).

Any UADEs, ADEs or SADEs will be summarized as well.

Device deficiencies collected on a separate eCRF form will also be summarized and indicate if any deficiencies resulted in any adverse events.

7 Poolability of Data

Analyses of the primary safety endpoint will be performed to assess the comparability of study sites. Sites with fewer than 5 subjects each will be included in summaries by site but excluded from poolability analysis.

LBAR Major Complications will be analyzed by Fisher's Exact test to assess if the Major Complication rates differ among study sites. If the study site rates differ ($p<0.15$) then additional analyses will be performed to explore the cause of the difference, in particular if the differences are caused by differences in some baseline factor.

8 Data Conventions and Missing Data

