Every effort will be undertaken to limit premature discontinuations and ascertain completeness of data collection throughout the course of the study. It is unlikely that there would be missing data for the LBAR Major complication endpoint as a 30 day follow-up visit is typically standard of care for TAVR patients; therefore all subjects with an attempted procedure are expected to be followed for at least 30 days. The 12 month follow up assessment will be conducted via phone; sites will ensure that subject contact details are on file correctly when concluding the 30 day visit.

No imputations will be made for missing endpoint data. All available data will be summarized for any summary provided the subject has a procedure attempt.

If an onset date for an AE is incomplete, every effort will be made by the clinical team to identify and collect a valid date from the site, but in case any are incomplete, then the following rules will be used:

- If the day of the month is missing, the first of the month will be used unless it precedes the procedure date. Then the procedure date will be used.
- If the month is missing the date of the procedure will be used.
- No year is expected to be missing as the follow-up is quite short, but the date of procedure will be used if missing the year.

9 Appendices:

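### SAP Section 8 dates an adverse event with a missing month or year to the procedure day even when the recorded parts of the date rule that out, so late events can be tabulated as Day 0

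*SAP*

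**What the plan says.** SAP Section 8 first requires a query: "every effort will be made by the clinical team to identify and collect a valid date from the site". Three rules cover onset dates that remain incomplete.

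- Day missing: "If the day of the month is missing, the first of the month will be used unless it precedes the procedure date"; in that case the procedure date is used.
- Month missing: "If the month is missing the date of the procedure will be used".
- Year missing: the SAP does not expect this, because it regards follow-up as short, "but the date of procedure will be used if missing the year".

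Onset dates feed the adverse event table in SAP 6.7. It reports a procedure-to-discharge period and then "discharge-30 days, 0-30 days, 31-60, 61-180 days, and 181-study exit". Protocol 6.3 and 15.3.4 separately plan an analysis of large bore access-site related (LBAR) Major and Minor complications after 30 days and up to 12 months. Protocol 9.2 has the 12-month call ask about problems in the treated leg or "a MANTA related adverse event between 30 days and 12 months".

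On missing endpoints, the same SAP section says "No imputations will be made for missing endpoint data" and "All available data will be summarized for any summary provided the subject has a procedure attempt". SAP 6.2 lets the primary report proceed when some of the 75 subjects have withdrawn before their 30-day visit.

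**The concern.** An imputation rule for a partial date should not contradict the part that is known. The day-missing rule respects this; the other two do not. The argument that follow-up is short does not rescue them. Follow-up runs to 12 months plus or minus 30 days, so it crosses a year end for practically every subject, and the recorded year is often informative.

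Partial dates are most plausible for events recalled by telephone at 12 months, which are the events meant to be late. Dating them to Day 0 removes them from the 31-60, 61-180 and 181-to-exit rows and adds them to the early rows. What is at stake is the description of late safety. A possible second effect is on the 30-day LBAR rate in the final report, if the imputed date is also used to sort those complications.

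**Working it through.** **1. The rules side by side.**

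| Missing part | Date assigned | Recorded parts used? |
|---|---|---|
| Day | first of the recorded month, not before the procedure | yes |
| Month | procedure date | no; recorded year ignored |
| Year | procedure date | no; recorded day and month ignored |

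**2. The rules applied to examples** (dates are illustrative assumptions).

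- Procedure 15 November 2022, onset recorded only as 2023. Earliest possible onset is 1 January 2023: 15 days left in November + 31 in December + 1 = Day 47. The rule gives Day 0.
- Procedure 15 June 2022, onset 10 March with no year. The only such date within follow-up is 10 March 2023: 15 days left in June + 184 for July to December + 31 + 28 + 10 = Day 268. The rule gives Day 0.

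**3. How often the recorded year alone excludes Days 0-30 (month missing).** Assumptions: procedures even over a 365-day year, onsets even over Days 31-365 (335 days). Let k be the number of days from the procedure to the next 1 January. The year excludes Days 0-30 when k is at least 31 (procedure on or before 1 December) and the onset day is k or later, which is 366 - k onset days.

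- Excluded pairs: sum over k = 31 to 365 of (366 - k) = 335 × 336 / 2 = 56,280.
- All pairs: 365 × 335 = 122,275.
- Share: 56,280 / 122,275 = 46.0%.

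For the other 54%, the earliest date that fits the recorded year still falls on Days 0-30. A better rule helps there only if some other lower bound exists.

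**4. The other two rules.** With the year missing but day and month recorded, only Day 365 shares its calendar date with a day in 0-30 (Day 0). The recorded parts therefore exclude Days 0-30 for 334 / 335 = 99.7% of onsets, but the SAP expects no missing years. The day-missing rule moves 49.1% of Day 31-60 onsets, and 4.4% of all Day 31-365 onsets, to Day 30 or earlier. It stays within the recorded month and is not the problem.

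**5. Conditional effect on LBAR results**, only if the imputed date does the sorting.

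- Registry figure (Protocol 3.4): 1 late event in 81, Major and Minor combined; exact 95% CI 0.03% to 6.7%. Times 150, this is about 1.9 late events (0.05 to 10.0), so one misdated event could be a large share. No late Major-only rate is given.
- One late Major event moved to Day 0 adds 1/150 = 0.67 points to the final 30-day rate. For example, 6/150 = 4.0% (exact 95% CI 1.5% to 8.5%) becomes 7/150 = 4.7% (1.9% to 9.4%). A Minor event adds nothing to it.

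**6. Timing of the primary report.** Protocol synopsis: 150 subjects over about 12 months. With even accrual (assumption), the 75th enrols at about month 6 and reaches Day 30 at about month 7. The first subject's 12-month call opens no earlier than about month 11.

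**7. Unknown 30-day outcomes (side point).** The planned 69 subjects reproduce: with an exact binomial test, 4 or fewer events of 69 has probability 0.0248 at 14.2% and 0.836 at 4.2%, and 69 is the first size from 50 upward with at least 80% power. Exact upper 97.5% bounds: 4/69 = 14.18%, 4/75 = 13.10% (both pass); 5/75 = 14.88% (fail). Now take losses as Binomial(75, loss rate), with a 4.2% event risk in known and lost subjects alike and lost subjects left out of the denominator. The chance that known cases pass while all 75 would show 5 or more events is 1.1% at 2% loss and 2.1% at 4% loss. With triple risk in lost subjects (12.6%, an assumption) it is 3.4% and 6.5%.

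**The case against.** The strongest reply is that the rules will rarely operate. They apply only after a failed query. Adverse event records are to carry awareness, onset and resolution dates, and serious events are reported within 24 hours of first knowledge (Protocol 11.6). Many LBAR Major events would be serious by definition, so one with no identifiable month is an edge case. All of this stands and limits the number affected, but it does not make the rule correct when it is used.

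The early date is also conservative for the primary test, since it can only add events to the 30-day count. That stands too, but the same shift flatters the late-safety rows.

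A reader might infer that misdated events certainly leave the after-30-day LBAR analysis and inflate the 30-day rate. The documents do not support that. Protocol 15.1.1 and 15.3.2 base the 30-day endpoint on adjudication by the Clinical Events Committee (CEC). SAP 6.7 leaves the exact process to the CEC charter, which is not among the documents. Protocol 9.2 already limits the 12-month inquiry to events after 30 days. Nothing states that the imputed date assigns LBAR events, and nothing states that it does not.

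A reader might also infer that the missing-endpoint plan is defective. It is not: the analysis set is defined, 75 subjects are taken where 69 are needed, and the pass limit is 4 events at either size.

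**Conclusion.** The month-missing and year-missing rules are wrong as written: they can assign a date that the recorded data exclude. The definite consequence is in the SAP 6.7 table, where such events move from the late rows to the Day 0 and 0-30 day rows, so late events are understated. For a missing month, the recorded year alone would have prevented this for about 46% of late onsets, under even procedure dates and even onsets over Days 31-365. The absolute number cannot be estimated, because the documents give no rate of incomplete dates; it is probably small.

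An effect on the after-30-day LBAR analysis and on the final report's 30-day rate is possible but undetermined, because the plan does not say whether the imputed date or the CEC's adjudication decides timing. The 75-subject primary report, on which SAP 6.2 intends approval to rest, is unlikely to be affected. The absence of a sensitivity line for unknown 30-day status is a minor, optional matter.

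**What to change.** In SAP Section 8, replace the month-missing and year-missing rules with one rule: *use the earliest date on or after the procedure that is consistent with every recorded date component and not later than the resolution or awareness date; use the procedure date only if nothing recorded excludes it.* Flag imputed dates in the listings. State that sorting LBAR events into the 30-day or later analysis follows CEC-adjudicated timing where available. If any imputed date changes the 30-day count, show the final-report rate under both the present rule and the new one.

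Optionally, if any of the 75 attempted subjects has unknown 30-day status, add a worst-case line beside the primary result and state whether such subjects stay in the denominator.

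The cost is a few lines of SAP text, a flag variable and at most one or two extra output lines. The downside is that the bounded rule can move events out of the 30-day count, which favours the device; that is why both versions should be shown. The rule will not correct late onsets whose recorded parts are compatible with Days 0-30, unless another lower bound is available.

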9.1 Appendix 1: Definitions of Relatedness of Adverse Events

Each reported AE will be assessed by the Investigator for its primary suspected relationship to the U/S guided MANTA VCD deployment/device or to the interventional procedure.

- Study AEs related to the interventional procedure (e.g., TAVR procedure) or closure of a non-target access site are considered Procedure-Related AEs.
- Study AEs related to the MANTA VCD and/or the U/S deployment method (in total, the closure procedure) are considered Device-Related AEs.
- Study AEs that are related to neither the interventional procedure nor use of the MANTA VCD are considered NOT related to the device or procedure.

The causal relationship of an AE to the device or procedure will be classified as follows:

Not related: relationship of the event to the device or procedure can be excluded when:

- the event is not a known side effect of the product category the device belongs to or of similar devices and procedures;
- the event has no temporal relationship with the use of the investigational device or the procedures;

- the event does not follow a known response pattern to the medical device (if the response pattern is previously known) and is biologically implausible;
- the discontinuation of medical device application or the reduction of the level of activation/exposure – when clinically feasible – and reintroduction of its use (or increase of the level of activation/exposure), do not impact on the event;
- the event involves a body-site or an organ not expected to be affected by the device or procedure
- the event can be attributed to another cause (e.g. an underlying or concurrent illness/ clinical condition, an effect of another device, drug, treatment or other risk factors);
- harms to the subject are not clearly due to use error;

In order to establish the non-relatedness, not all the criteria listed above might be met at the same time, depending on the type of device/procedures and the adverse event.

Possible: relationship of the event with use of the investigational device or the procedure is weak but cannot be ruled out completely. Alternative causes are also possible (e.g., an underlying or concurrent illness/ clinical condition or/and an effect of another device, drug or treatment). Cases where relatedness cannot be assessed or no information has been obtained should also be classified as possible.

Probable: relationship of the event with use of the investigational device or the procedure seems relevant and/or the event cannot reasonably be explained by another cause, but additional information may be obtained.

Causal relationship: the event is associated with the investigational device or procedure beyond a reasonable doubt when:

- the event is a known side effect of the product category the device belongs to or of similar devices and procedures;
- the event has a temporal relationship with investigational device use/application or procedures;
- the event involves a body-site or organ that:
 - the investigational device or procedure is applied to
 - The investigational device or procedure have an effect on;
- the event follows a known response pattern to the medical device (if the response pattern is previously known);
- the discontinuation of medical device application (or reduction of the level of activation/exposure) and reintroduction of its use (or increase of the level of activation/exposure), impact on the event (when clinically feasible);
- other possible causes (e.g., an underlying or concurrent illness/ clinical condition or/and an effect of another device, drug or treatment) have been adequately ruled out;
- harm to the subject is due to error in use.

In order to establish the relatedness, not all criteria listed above might be met at the same time depending on the type of device/procedures and the serious event.

9.2 Appendix 2: Definitions from the Protocol

Adjunctive Compression: Compression methods (including sandbags, compression bandages, and light manual pressure) for controlling cutaneous or subcutaneous oozing.

Adverse Device Effect (ADE): Adverse event (see definition below) resulting from insufficient or inadequate instructions for use, deployment, implantation, installation, or operation, or any malfunction of the investigational medical device. This definition includes any event resulting from use error or from intentional misuse of the investigational medical device.

Adverse Event (AE): Any untoward medical occurrence, unintended disease or injury, or untoward clinical signs (including abnormal laboratory findings) in subjects, users or other persons, whether or not related to the investigational medical device. Note: This definition includes events related to the investigational medical device. This definition includes events related to the procedures involved. For users or other persons, this definition is restricted to events related to investigational devices.

Ambulation Success: A subject will be considered an Ambulation Success if a previously ambulatory patient (until day of TAVR) is able to ambulate for at least 20 feet/6 meters without re-bleeding.

Bleeding: Definitions used in conjunction with definitions of LBAR Major complications and LBAR Minor complications below. As defined in the VARC-2 Clinical Guidelines:

Life-threatening or disabling bleeding:

- Fatal bleeding (BARC type 5) OR
- Bleeding in a critical organ, such as intracranial, intraspinal, intraocular, or pericardial necessitating pericardiocentesis, or intramuscular with compartment syndrome (BARC type 3b and 3c) OR
- Bleeding causing hypovolemic shock or severe hypotension requiring vasopressors or surgery (BARC type 3b) OR
- Overt source of bleeding with drop in hemoglobin ≥ 5 g/dL or whole blood or packed red blood cells (RBCs) transfusion ≥ 4 units* (BARC type 3b)

Major bleeding (BARC type 3a):

- Overt bleeding either associated with a drop in the hemoglobin level of at least 3.0 g/dL or requiring transfusion of 2 or 3 units of whole blood/RBC, or causing hospitalization or permanent injury, or requiring surgery AND
- Does not meet criteria of life-threatening or disabling bleeding

Minor bleeding (BARC type 2 or 3a, depending on the severity):

- Any bleeding worthy of clinical mention (e.g., access site hematoma) that does not qualify as life-threatening, disabling, or major

Cachexia: Defined as very thin, or body mass index <20 kg/m².

Device Deficiency: Inadequacy of a medical device with respect to its identity, quality, durability, reliability, safety or performance; includes device malfunctions, use errors and inadequate labeling.

Ecchymosis: An area of subcutaneous discoloration caused by the extravasation of blood into the subcutaneous tissue not associated with a definable, palpable subcutaneous mass.

Hematoma: An expanding or non-expanding subcutaneous mass of blood greater than 2 cm in its longest axis, confirmed by U/S.

Hemostasis (Time to): The elapsed time between MANTA deployment (withdrawal of sheath from artery and first observed and confirmed arterial hemostasis (no or minimal subcutaneous oozing and the absence of expanding or developing hematoma). Time to Hemostasis should be inclusive of any time that manual or mechanical pressure is applied specifically to stop arterial bleeding. Do not include time spent when light digital or mechanical pressure is done to treat oozing, or if short manual compression is done as a preventative measure as part of standard of care.

Large Bore Access-sire Related Major Vascular (LBAR Major) Complications: Adapted from the VARC-2 Clinical Guidelines¹:

- Access site or access-related vascular injury (dissection, stenosis, perforation, rupture, arterio-venous fistula, pseudoaneurysm, hematoma, irreversible nerve injury, compartment syndrome, percutaneous closure device failure) leading to death, life threatening or major bleeding, visceral ischemia, or neurological impairment OR
- Distal embolization (noncerebral) from a vascular source requiring surgery or resulting in amputation or irreversible end-organ damage OR
- The use of unplanned endovascular or surgical intervention associated with death, major bleeding, visceral ischemia or neurological impairment OR
- Any new ipsilateral lower extremity ischemia documented by patient symptoms, physical exam, and/or decreased or absent blood flow on lower extremity angiogram OR
- Surgery for access site-related nerve injury OR
- Permanent access site-related nerve injury

Large Bore Access-site Related VARC-2 Minor Vascular Complication (LBAR Minor): Adapted from VARC-2 Clinical Guidelines:

- Access site or access-related vascular injury (dissection, stenosis, perforation, rupture, arterio-venous fistula, pseudoaneurysms, hematomas, percutaneous closure device failure) not leading to death, life-threatening or major bleeding, visceral ischemia, or neurological impairment OR
- Distal embolization treated with embolectomy and/or thrombectomy and not resulting in amputation or irreversible end-organ damage OR
- Any unplanned endovascular stenting or unplanned surgical intervention not meeting the criteria for a major vascular complication OR
- Vascular repair or the need for vascular repair (via surgery, U/S-guided compression, transcatheter embolization, or stent-graft) OR

¹ The Major Vascular Complications definition from the VARC-2 guidelines was adapted as follows: The first bullet of the definition ("Any aortic dissection, aortic rupture, annulus rupture, left ventricle perforation, or new apical aneurysm/pseudoaneurysm OR") was deleted from the definition used in this protocol, as these adverse events are entirely unrelated to the femoral access site

- Percutaneous closure device failure - Failure of a closure device to achieve hemostasis at the arteriotomy site leading to alternative treatment (other than manual compression or adjunctive endovascular ballooning)

Morbid Obesity: Defined by the position of the access needle whereby less than one third of the access needle is above the skin line indicating the subject is morbidly obese, or body mass index >40 (weight in kg divided by square of height in meters).

Nerve Injury: Any ipsilateral transient or permanent sensory or motor neurologic deficit of the femoral nerve, or anterior or lateral cutaneous femoral nerve, or evidence of sacral plexus injury from documented retroperitoneal bleeding, as determined by a neurologist.

Oozing: Bleeding of a cutaneous or subcutaneous origin that can be controlled with the application of light compression methods (sandbags, compression bandages, or light manual pressure) and which do not apply sufficient compression to control arterial bleeding. Light manual compression may be substituted by light compression from a mechanical device.

Operators: Medical personnel trained and qualified to the clinical use of the medical device (MANTA VCD)

Pre-existing Hematoma: An expanding or non-expanding subcutaneous mass of blood present prior to the start of the access site closure.

Procedure Time: Defined as elapsed time from initial skin break (first needle insertion) to time when the post-deployment angiogram is completed.

Serious Adverse Device Effect (SADE): An Adverse Device Effect that has resulted in any of the consequences characteristic of a Serious Adverse Event.

Serious Adverse Event (SAE): An SAE is an Adverse Event that:

- Led to death,
- Led to serious deterioration in the health of the subject, that either resulted in
 - a life-threatening illness or injury, or
 - a permanent impairment of a body structure or a body function, or
 - in-patient or prolonged hospitalization, or
 - medical or surgical intervention to prevent life-threatening illness or injury or permanent impairment to a body structure or a body function,
- Led to fetal distress, fetal death or a congenital abnormality or birth defect.

Note: Planned hospitalization for a pre-existing condition, or a procedure required by this protocol, without serious deterioration in health, is not considered a serious adverse event.

Severe Peripheral Vascular Disease: Any of the following:

- Severe claudication when ambulating <100 feet
- Weak or absent pulses in the affected limb
- ABI <0.5 at rest
- Known stenosis >50% in the iliac or femoral artery on the affected side
- Prior vascular bypass surgery involving the affected femoral artery

Stable Access Site Status: Defined as ability to walk at least 20 feet/6 meters, freedom from orthostatic hypotension [defined as stable blood pressure and heart rate after ambulating], ability to void and a stable access site without bleeding or expansion of a prior hematoma.

Technical Success: A subject will be considered a Technical Success if percutaneous vascular closure is obtained with the MANTA VCD without the use of unplanned endovascular or surgical intervention.

Time to Ambulation: The elapsed time between MANTA VCD deployment (withdrawal of MANTA VCD sheath from artery) and when ambulation is first achieved (subject standing and walking at least 20 feet/6 meters without re-bleeding).

Time to Hemostasis: The elapsed time between MANTA deployment (withdrawal of sheath from artery) and first observed and confirmed arterial hemostasis (no or minimal subcutaneous oozing and the absence of expanding or developing hematoma). Time to Hemostasis should be inclusive of any time that manual or mechanical pressure is applied specifically to stop arterial bleeding. Do not include time spent when light digital or mechanical pressure is done to treat oozing, or if short manual compression is done as a preventative measure as part of standard of care.

Treatment Success: A subject will be considered a Treatment Success if he/she has Time to Hemostasis ≤10 minutes and has no LBAR Major complications within 30 days.

Unanticipated Adverse Device Effect (UADE): Any serious adverse effect on health or safety or any life-threatening problem or death caused by, or associated with, a device, if that effect, problem, or death was not previously identified in nature, severity, or degree of incidence in the investigational plan or application (including a supplementary plan or application), or any other unanticipated serious problem associated with a device that relates to the rights, safety, or welfare of subjects.

Unanticipated Serious Adverse Device Effect (USADE): A Serious Adverse Device Effect, which by its nature, incidence, severity or outcome has not been identified in the current version of the risk analysis report. Note: An anticipated serious adverse device effect is a serious adverse device effect which by its nature, incidence, severity or outcome has been identified in the risk analysis report.

10 References

3. Van Mieghem N. MANTA Closure in TAVR - The Marvel Prospective Registry. Presented at: Cardiovascular Research Technologies (CRT); Feb 25, 2020, Maryland USA.
